#### **PRO 10 Protocol Summary of Changes**

#### AMENDMENT NUMBER 2

#### AMENDMENT DATE 23 January 2018

#### **Global changes**

Cabozantinib has been added as a possible IP

Minor editorial and formatting changes are not detailed in this Summary of Changes

CONFIDENTIAL

STUDY DRUG(S): REGORAFENIB/AFATINIB/CABOZANTINIB INNOVATIONS STUDY NUMBER: PRO 10 FINAL PROTOCOL DATE: 6 MAY 2016 Amendment Number 2:23 January 2018 SARAH CANNON DEVELOPMENT

# **PRO 10 PROTOCOL SYNOPSIS**

Title of Study:	A phase II study to evaluate the activity of commercially available molecularly matched targeted therapies in selected tumor types based on genomic alterations			
Sarah Cannon Development Innovations Study Number:	PRO 10; ONC-2014-138 (Bayer); PRO10/1200.262 (Boehringer Ingelheim)/Pro 10 Exelixis			
Sponsor:	Sarah Cannon Development Innovations, LLC – Nashville – TN			
Study Duration:	Enrollment will occur over approximately 18 months. The total duration of the study is planned to be approximately 27 months.			
Study Centers:	This study will be conducted at approximately 20 sites.			
Number of Patients:	Up to 160 patients are planned to be enrolled in this study.			
	
 
The primary objective of this study is to:
 
Determine the overall response rate (Complete Response [CR] + Partial Response [PR]) in each patient population receiving targeted therapy based on relevant genomic alterations.
 
Secondary Objectives The secondary objectives of this study are to: 
 
Evaluate the clinical benefit rate (CR + PR + stable disease [SD] ≥ 6 months) in each patient population receiving targeted therapy based on relevant genomic alterations.
 
 
 
Determine the time to treatment failure (measured from the first day of treatment until the patient is removed from study for toxicity, disease progression, patient choice, or death) in each patient population receiving targeted therapy based on relevant genomic alterations.
 
To determine the progression free survival (PFS) in each patient population receiving targeted therapy based on relevant genomic alterations.
 
			
Study Design:	This four-arm pilot phase II study will evaluate the preliminary antitumor activity of selected commercially available molecularly matched targeted therapies in patients who have failed first line treatment for one of the following tumor types: (1) non-small cell lung cancer, (2) urothelial carcinoma, (3) non-colon gastrointestinal cancers, and (4) upper aerodigestive tract cancers. Patients will be profiled with next-generation sequencing technology results known prior to consideration for enrollment on this protocol. Patients with the specified tumor types demonstrating one of the genomic alterations described in Table 1 may be assessed for protocol eligibility and treatment. All eligible patients will receive one of the FDA-approved targeted agents at the recommended dose outlined in Table 2. Patients with a genomic alteration that is not described in Table 1 but is covered by a targeted agent in Table 2 will also be eligible. Dose modifications will be implemented based on criteria outlined in the product package insert for each individual agent. Patients will be re-evaluated for treatment response after receiving 8 weeks of oral therapy (with the exception of regorafenib which is dosed intermittently for 21 out of every 28 days). Response to therapy will be assigned using RECIST v1.1 (see Section E). Patients who have CONFIDENTIAL			

CONFIDENTIAL

STUDY DRUG(S): REGORAFENIB/AFATINIB/CABOZANTINIB INNOVATIONS STUDY NUMBER: PRO 10 FINAL PROTOCOL DATE: 6 MAY 2016 Amendment Number 2:23 January 2018 SARAH CANNON DEVELOPMENT

	
 
objective response (OR) or stable disease (SD) will continue treatment with re-evaluations every 8 weeks, until the time of tumor progression or intolerable treatment-related side effects. If a patient was not profiled with Foundation One® prior to study enrolment, Sarah Cannon Development Innovations shall use reasonable efforts to collect and send to Foundation Medicine adequate tumor tissue meeting the tissue specimen requirements for Foundation One® for retrospective profiling that will be completed and compared to the profiling report provided at study entry.
 
A total of 160 patients are planned to be enrolled on the trial (40 patients per study arm).
 
		
Study Drugs,	The study drugs are outlined in Table 2 and will be provided to the sites. The initial dosing		
Doses, and Modes	regimen for each agent is outlined in Section 8.1. All drugs are to be administered orally		
of Administration:	according to the dosing guidelines in the product package insert. Copies of the product		
Inclusion Criteria:	package inserts are included in Appendices G and H.		
Inclusion Criteria:	1. Patients with a histologically or cytologically confirmed diagnosis of one of the following tumor types whose disease has progressed following one line of standard therapy and/or for which no standard treatment is available that has been shown to prolong survival:		
	a. Non-small cell lung cancer		
	b. Urothelial carcinoma		
	c. Non-colon gastrointestinal cancers (including hepatobiliary, pancreatic, and gastroesophageal tumors)		
	d. upper aerodigestive tract cancers (including lip, tongue, salivary gland, gum, oral cavity, mouth, tonsils, oropharynx, nasopharynx, nasal cavity, sinus, and larynx tumors)		
	2. Patients must have a predefined genomic alteration included in Table 1 that can be targeted with one of the FDA-approved targeted agents listed in Table 2. Patients with a genomic alteration that is not described in Table 1 but is covered by a targeted agent in Table 2 will also be eligible.		
	3. Patients must have measurable disease as measured by Response Evaluation Criteria in Solid Tumors (RECIST) criteria version 1.1 (Appendix E).		
	4. Patients must have an Eastern Cooperative Oncology Group (ECOG) Performance Status score of 0 or 1 (Appendix A).		
	5. Age greater than or equal to 18 years.		
	6. Adequate hematologic function defined as:		
	- Absolute neutrophil count (ANC) $\geq 1500/\mu L$		
	- Platelets $\geq$ 75,000/µL		
	7. Adequate liver function defined as:		
	- Alanine aminotransferase (ALT) and aspartate aminotransferase (AST) $\leq 2.5 \text{ x}$ the upper limit of normal (ULN) or $\leq 5.0 \text{ X}$ ULN if liver metastases present		
	
 
Total bilirubin ≤1.5 x ULN (unless the patient has Grade 1 bilirubin elevation due to Gilbert's disease or a similar syndrome involving slow conjugation of bilirubin)
 
		

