Statistical Methodology	The design of this trial uses an exact single-stage design for each of the four arms. (A'Hern 2001) For this investigation, it has been determined that an ORR (CR + PR) of 10% or worse has low activity in line with standard of care. An ORR of 25% (or better) is considered to indicate interesting activity. Using a one-sided alpha of 5% and power of 80%, 40 evaluable patients will be required in each arm. A minimum of 8 responders in a particular arm would indicate that the corresponding tumor type would be worthy of further investigations.

CONFIDENTIAL

STUDY DRUG(S): REGORAFENIB/AFATINIB/CABOZANTINIB INNOVATIONS STUDY NUMBER: PRO 10 FINAL PROTOCOL DATE: 6 MAY 2016 Amendment Number 2:23 January 2018 SARAH CANNON DEVELOPMENT

		STUDY TREAT	MENT (Cycles repo	eated every 28 days	FOLLOW-UP
ASSESSMENTS	PRE- TREATMENT	Cycle 1 Day 1ª	Cycle 1 Day 15	Cycles 2+h	End of Study Evaluation i
	Baseline a		,		
Tests and Observations					
Informed consent	Х				
Medical history	Х	Х			Х
Physical exam (including vital signs) b	Х	Х	Xj	Х	Х
ECOG PS	Х	Х		Х	Х
Concomitant medication review	Х	Х	Х	Х	Х
Adverse event evaluation			Х	Х	Х
Study Drug Compliance Review c			Х	Х	Х
Laboratory Observations					
CBC, 3-part differential, and platelets d	Х	Х	Х	Х	Х
CMP plus magnesium d	Х	Х	Х	Х	Х
PT/INR/PTT	Х				
Serum or urine pregnancy test e	Х	Х		Х	
Disease Assessment					
Tumor marker (if applicable)	Х			Х	
CT Scan chest/abdomen/pelvisf	Х			Х	
MRI or CT Scan of Brain g	Х				

STUDY DRUG(S): REGORAFENIB/AFATINIB/CABOZANTINIB FINAL PROTOCOL DATE: 6 MAY 2016 Amendment Number 2:23 January 2018 CONFIDENTIAL SARAH CANNON DEVELOPMENT INNOVATIONS STUDY NUMBER: PRO 10 VERSION 3

Page 11 of 53

- a Baseline procedures including medical history, physical examination, 12-lead ECG, ECOG PS, and laboratory tests should be done  $\leq$ 7 days prior to initiation of treatment. However, if these initial examinations are obtained within 72 hours of Cycle 1 Day 1 they do not have to be repeated.
- b Physical examination will include measurements of height (pretreatment visit only), weight, and vital signs.

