- c On day 15 of cycle 1 and at the beginning of each subsequent treatment cycle, study drug compliance should be reviewed with the patient and a sufficient supply of drug should be dispensed to the patient to take at home. A final drug compliance assessment should be done at the End of Treatment visit (if applicable) and any remaining drug should be retrieved from the patient.
- d May be done up to 72 hours prior to day 1 of each treatment cycle.
- e Serum or urine pregnancy test required on day 1 of each treatment cycle in women of child-bearing potential only.
- f CT scan s of the chest/abdomen/pelvis required at baseline. Scans will be repeated every 2 cycles. Only abnormal scans need to be repeated after baseline.
- g Head CT or MRI scan required at baseline for patients with a history of treated brain metastases only.
- h There is a +/- 7 day window on day 1 of all subsequent cycles to accommodate scheduling issues.
- i Patients must be followed for AEs for 30 calendar days after the last dose of study drug. Patients who have not progressed at the time of study discontinuation will be followed for disease assessment only every 3 months ( $\pm 1$  month) until disease progression.
- j. On CD15, vital signs only. No physical exam is required on this visit.

STUDY DRUG(S): REGORAFENIB/AFATINIB/CABOZANTINIB FINAL PROTOCOL DATE: 6 MAY 2016 Amendment Number 2:23 January 2018 CONFIDENTIAL SARAH CANNON DEVELOPMENT INNOVATIONS STUDY NUMBER: PRO 10 VERSION 3

Sarah Cannon Development Innovations Contact Information:	Sarah Cannon Development Innovations [name] [name] [contact]
Study Chair:	[name] Sarah Cannon Development Innovations [name] [name] [contact]
Safety Dept. [contact]
Safety Dept. Email:	[contact]
Regulatory Phone # Regulatory Email:	[name] [contact]

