## **1.2** Targeted Treatment for Known Genomic Alterations

Table 2 lists the FDA-approved targeted agents that will be utilized in this study as matched therapies for the genomic alterations.

Approved Drug	Targets Listed in Package Insert	Manufactu rer	Recommended Dose
Regorafenib (Stivarga)	RET, VEGF1-3, KIT, PDGFR- $\alpha$ and $\beta$ , FGFR1- 2, TIE2, DDR2, Trk2A, Eph2A, RAF-1, BRAF, SAPK2, PTK5, Abl	Bayer	160 mg once daily for the first 21 days of each 28 day cycle
Afatinib (Gilotrif™)	EGFR, HER2, HER4	Boehringer Ingelheim	40 mg once daily
Cabozantinib (Cabometyx TM )	MET, VEGFR1-3, AXL, RET, ROS1, TYRO3, MER, KIT, TRKB, FLT- 3, TIE2	Exelixis, Inc	60 mg once daily

 Table 2: FDA-Approved Targeted Agents

All drugs will be administered according to the recommended package insert dose. Dosing will be continuous daily for all drugs except regorafenib, which is dosed for 21 days out of every 28 days. For the purposes of the study, a treatment cycle will be defined as 28 days. Recommended dose modifications for treatment-related toxicities are outlined in the package insert prescribing information. Patients will return to clinic on day 1 of every treatment cycle for evaluation and scans will be performed every 2 cycles for disease assessment. The product package inserts for the individual drugs are included in Appendices G and H.

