## 5. STUDY DESIGN

This four-arm pilot phase II study will evaluate the preliminary antitumor activity of selected commercially available molecularly matched targeted therapies in patients who have failed first line treatment for one of the following tumor types: (1) non-small cell lung cancer, (2) urothelial carcinoma, (3) non-colon gastrointestinal cancers, and (4) upper aerodigestive tract cancers. Patients will be profiled with next-generation sequencing technology results known prior to consideration for enrollment on this protocol. Patients with the specified tumor types demonstrating one of the genomic alterations described in Table 1 may be assessed for protocol eligibility and treatment. Patients with a genomic alteration that is not described in Table 1 but is covered by a targeted agent in Table 2 will also be eligible. All eligible patients will receive one of the FDA-approved targeted agents at the recommended dose outlined in Table 2. Dose modifications will be implemented based on criteria outlined in the product package insert for each individual agent. Patients will be re-evaluated for treatment response after receiving 8

CONFIDENTIAL

STUDY DRUG(S): REGORAFENIB/AFATINIB/CABOZANTINIB INNOVATIONS STUDY NUMBER: PRO 10 FINAL PROTOCOL DATE: 6 MAY 2016 AMENDMENT NUMBER 2:23 JANUARY 2018 SARAH CANNON DEVELOPMENT

weeks of oral therapy (with the exception of regorafenib which is dosed intermittently for 21 out of every 28 days). Response to therapy will be assigned using RECIST v1.1 (see Appendix E). Patients who have objective response (OR) or stable disease (SD) will continue treatment with re-evaluations every 8 weeks, until the time of tumor progression or intolerable treatment-related side effects. If a patient was not profiled with Foundation One® prior to study enrolment, Sarah Cannon Development Innovations shall use reasonable efforts to collect and send to Foundation Medicine adequate tumor tissue meeting the tissue specimen requirements for Foundation One® for retrospective profiling that will be completed and compared to the profiling report provided at study entry.

A total of 160 patients are planned to be enrolled on the trial (40 patients per study arm).

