## 5.2 Treatment Duration

Patients will continue to receive treatment until disease progression, the patient requests to discontinue treatment, or the treating physician feels it is in the best interest of the patient to discontinue.

For the purposes of the study, a treatment cycle is defined as 28 days. Patients will be evaluated for toxicity at the start of each cycle. Every 2 cycles restaging will occur with imaging, laboratory tests will be assessed as defined in Appendix E.

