#### CONFIDENTIAL

STUDY DRUG(S): REGORAFENIB/AFATINIB/CABOZANTINIBSARAH CANNON DEVELOPMENTINNOVATIONS STUDY NUMBER: PRO 10FINAL PROTOCOL DATE: 6 MAY 2016VERSION 3AMENDMENT NUMBER 2:23 JANUARY 2018VERSION 3

- CMP plus magnesium (may be done up to 72 hours prior to treatment)
- Serum or urine pregnancy test in women of child-bearing potential only
- Tumor markers (if applicable)
- CT scans of chest, abdomen, and pelvis (if abnormal at baseline) [Every 2 cycles]

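### After one permitted 28-day toxicity hold on afatinib or cabozantinib, the therapy-received wording moves the first tumor scan from Day 56 to nominal Day 84; anchoring scans to the calendar is a cheap fix

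*Combined protocol and SAP*

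**What the plan says.** **First evaluation.** The Study Design text of the Synopsis, repeated in Section 5, reads "Patients will be re-evaluated for treatment response after receiving 8 weeks of oral therapy". A parenthesis then excepts regorafenib because it is given 21 days in 28, but states no timing for it.

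**Later evaluations.** Section 5 says that patients with response or stable disease "will continue treatment with re-evaluations every 8 weeks, until the time of tumor progression".

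**Cycle-based wording.** Section 1.2 has patients return "on day 1 of every treatment cycle for evaluation and scans will be performed every 2 cycles for disease assessment". Section 5.2 says "Every 2 cycles restaging will occur with imaging", and footnote f of the schedule says "Scans will be repeated every 2 cycles". Section 7.3.1 lists CT among the Day 1 procedures, every 2 cycles. Sections 1.2 and 5.2 define a cycle as 28 days.

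**Delays and windows.** Section 6 takes a patient off study only when a toxicity delay exceeds 28 days, and sets no limit on the number of delays. Footnote h gives a ±7 "day window on day 1 of all subsequent cycles to accommodate scheduling issues". It applies to the Cycles 2+ column, which holds the on-treatment CT.

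**Endpoints that use scan dates.** Section 10.2.2 measures PFS from Day 1 to RECIST progression or death, and counts stable disease of at least 6 months toward the clinical benefit rate (CBR).

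**The concern.** A count of therapy received stops during a hold, while a calendar does not. Whether a cycle count stops depends on whether Day 1 of the next cycle moves, and the protocol does not say. The wordings agree only for a patient who is never held. Once a hold occurs, two sites could scan the same patient weeks apart and both be following the text.

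The later scans carry two wordings, every 8 weeks and every 2 cycles, which can diverge in the same way.

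Three things are at stake. Recorded PFS would depend partly on toxicity, as would 6-month stable disease. A held patient whose disease has already progressed might also wait longer to be found. These are secondary, descriptive, single-arm endpoints.

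**Working it through.** **The plan's own figure.** Section 10 gives 40 patients per arm, at least 8 responders, 10% against 25%, one-sided 5% and 80% power. The exact binomial gives P(X ≥ 8 | 40, 0.10) = 0.0419 and P(X ≥ 8 | 40, 0.25) = 0.8180. At n = 39 power is 0.7945, so the design reproduces. No scan date enters it.

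**Day of the first scan.** For a continuously dosed drug and a total hold of d days before that scan:
- therapy received: 56 + d
- fixed calendar (2 × 28 days): 56
- cycles whose Day 1 moves with the hold: 56 + d

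| Hold | Calendar | Therapy received |
|---|---|---|
| 0 | 56 | 56 |
| 7 days | 56 | 63 |
| 14 days | 56 | 70 |
| 28 days | 56 | 84 |
| two of 28 days | 56 | 112 |

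With the ±7 day window, the one-hold row becomes Day 49–63 against Day 77–91. The two ranges do not overlap, so the window cannot reconcile the readings. For regorafenib, two cycles hold 42 dosing days, and the 56th dosing day would be Day 70 even without a hold. The exception takes the drug out of that rule, so Day 70 is not a protocol date.

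**Effect on recorded outcomes.** The documents give no PFS median and no hold rate, so both are assumed. PFS is exponential with S(t) = 2^(−t/m) and m = 8.7, 13 or 17.3 weeks. All events are found at scans. A share p of the arm has one full 28-day hold before the first scan, and scans then follow every 8 weeks.

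Mean recorded PFS = f + 8 × Σ S(f + 8k) over k ≥ 0, with f = 8 (calendar) or 12 (slipped). The arm shift in days is 7 × p × the difference in weeks. For m = 8.7 and p = 0.3 this is 7 × 0.3 × 1.55 = 3.3.

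| m (weeks) | Mean, calendar | Mean, slipped | Difference | Arm shift in days at p = 0.1 / 0.3 / 0.5 |
|---|---|---|---|---|
| 8.7 | 16.97 | 18.52 | 1.55 | 1.1 / 3.3 / 5.4 |
| 13 | 23.04 | 24.15 | 1.11 | 0.8 / 2.3 / 3.9 |
| 17.3 | 29.17 | 30.04 | 0.86 | 0.6 / 1.8 / 3.0 |

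The recorded arm median is the first scan week at which (1 − p) × S_calendar + p × S_slipped ≤ 0.5, both being step functions. For the three values of m:
- p = 0 and p = 0.1: 16, 16 and 24 weeks
- p = 0.3: 12, 16 and 24
- p = 0.5: 12, 16 and 20

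For 6-month stable disease, assume it needs a progression-free scan at or after week 26. The calendar grid first meets this at week 32, the 28-day slip at week 28 and a 7-day slip at week 33.
- S(32) = 0.078, 0.182, 0.277; S(28) = 0.107, 0.225, 0.326; S(33) = 0.072, 0.172, 0.267.
- 40 × p × (S(28) − S(32)): 0.12, 0.17, 0.19 patient at p = 0.1; 0.35, 0.52, 0.58 at 0.3; 0.59, 0.86, 0.96 at 0.5.
- A 7-day slip at p = 0.3 goes the other way: −0.07, −0.11, −0.13.

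Responders count toward CBR whatever their duration, so these counts are upper values.

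**Detection.** The share of held patients already progressed by Day 56 is 1 − S(8) = 0.471, 0.347, 0.274. Without an unscheduled scan they would be found 28 days later.

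**The case against.** The operative text leans one way. Four places say every 2 cycles, a cycle is defined as 28 days with no provision for lengthening it, and Section 5.1.1 has missed doses skipped rather than made up. On that reading the first scan is at Day 56 ± 7, and the therapy-received sentence is loose wording for about 8 weeks on treatment. Appendix E, to which Section 9 sends response evaluation, and the package inserts that govern dose changes are not in the public text and might settle the matter.

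The sizes are also slight. Mean PFS is not a planned summary; Sections 10.2 and 10.2.2 plan Kaplan-Meier medians. The median can fall while the mean rises, because two scan grids are being mixed. With 40 patients the sampling SD of mean PFS is about 13.5, 21 and 28 days under the same model, against shifts of 0.6 to 5.4 days. The binomial SD of the 6-month count is 1.7 to 2.8 patients, against at most 0.96. Held patients are still examined on Day 1 of each cycle.

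The points on size stand. The lean toward a calendar is real but not decisive: the therapy-received sentence appears twice, Section 5.1.1 concerns missed doses rather than toxicity holds, and nothing available says that Day 1 stays put during a hold. Section 7.4 ties off-treatment assessments to the date of last dose; on-treatment scans have no such anchor.

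A reader might infer more than the text supports:
- **Three competing rules for the first scan.** There are two; the 8-week interval applies to patients who continue after it.
- **Day 84 as the latest possible date.** It is the nominal day after one hold. The window reaches Day 91, and repeat holds go later.
- **The same slip for all three drugs.** Regorafenib is excepted and moves only if its cycle Day 1 moves.

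**Conclusion.** The point holds as a low-priority wording defect. For afatinib and cabozantinib, following the stated therapy-received rule through one permitted 28-day hold moves the first scan from Day 56 to nominal Day 84. No available section fixes on-treatment scans to the calendar. Scan timing can therefore depend on toxicity and on how a site reads the text.

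The effect on descriptive PFS and on 6-month stable disease is small and not consistent in direction. Progression in a held patient may be detected up to 28 days later. These sizes rest on the assumed exponential medians, the assumed hold rates and every event being found by scan; if some events are deaths, the effects are overstated.

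A reader might go on to infer that the response decision is compromised or that the drugs are compared unfairly. The documents do not support either: the 8-of-40 rule is not shown to be affected, and no between-drug comparison is planned.

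**What to change.** In the Synopsis, Sections 1.2, 5, 5.2 and 7.3.1 and footnote f, state that tumor assessments occur every 8 calendar weeks (±7 days) from Cycle 1 Day 1 for all three drugs, regardless of dose interruptions or cycle delays. Tie the window to the calendar scan date rather than to cycle Day 1. Delete the regorafenib exception from the assessment sentence, since Table 2 already gives its dosing.

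This changes wording only and adds no procedure. There are two downsides. In held patients some scans will not coincide with a Day 1 visit. A scan may also follow a period off drug: if Cycle 2 is held for 28 days, the Day 56 scan follows one cycle on drug and 28 days off. Progression seen then ends treatment under Section 3.3 after one cycle of exposure.
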